Protocol Number:	LDN 6729
Protocol Title:	Synergistic Enteral Regimen for Treatment of the Gangliosidoses (Syner-G)
Study Chair:	[name]
Statistician:	[name].
Consortium:	Lysosomal Disease Network
Participating Sites:	University of Minnesota
Activation Date:	02/24/2016
Sample Size:	A total of 30 infants or children: 
 • 5 patients with infantile Tay-Sachs disease • 5 patients with juvenile Tay-Sachs disease • 5 patients with infantile Sandhoff disease • 5 patients with juvenile Sandhoff disease • 5 patients with infantile GM1 gangliosidosis • 5 patients with juvenile GM1 gangliosidosis
Target Enrollment Period:	Rolling enrollment of patients with infantile or juvenile gangliosidosis over the next five years; whenever possible, making one yearly visit to the University of Minnesota
Study Design:	Interventional study
Therapeutic Agent:	Miglustat
FDA IND Status:	IND 127636 Active
Phase:	Phase II
Methodology:	Combination enteral therapy
Study Design:	Single arm, open-label treatment study
Study Duration:	5 Years
Primary Study Objective:	To assess the impact of Syner-G therapy on overall survival in patients with infantile and juvenile forms of gangliosidosis
Secondary Study Objective:	To evaluate effects of Syner-G therapy in pediatric gangliosidoses patients on their neuro-developmental status
Study Population and Main Eligibility/Exclusion Criteria:	
Study Population: Any infant or juvenile patient with a gangliosidosis disease.
 
Inclusion Criteria:
 
 1.) Subjects must have a documented infantile or juvenile gangliosidosis disease. 2.) Age: 17 years or less at time of enrollment. 3.) Subjects and their caregivers must work closely with their University of Minnesota ketogenic diet team, and with their local ketogenic diet team, which must include a ketogenic dietician and a neurologist trained in the ketogenic diet. 
Exclusion Criteria:
 
 1.) A desire to not participate. 2.) Children with severe renal impairment will not be enrolled in this study. 3.) Post-pubertal females who are pregnant, or who are unwilling to use highly-effective methods to prevent pregnancy, will be excluded from this study. 4.) Breast-feeding females will be excluded from this study. 5.) Subjects who have an allergy to miglustat or any of the

	components within the drug product will be excluded from this study.
Primary Outcome Measures:	Retrospective and prospective data will be collected, that include: Overall participant survival, evaluated based on chronological age at time of death or at conclusion of study, whichever occurs first.
Secondary Outcome Measures:	Retrospective and prospective data will be collected, that include: The rate of change (i.e., slope) in neurocognitive functioning over the duration of follow-up will be determined; and will also be compared to available published natural history data. This analysis will be conducted separately for each of the two disease sub-types: infantile and juvenile. The primary neurocognitive measure for both pediatric groups is age-equivalent scores of the Bayley Scales of Infant and Toddler Development for expressive communication, receptive communication, fine motor skills and gross motor skills. The secondary neurocognitive measure for both pediatric groups is standard and age-equivalent scores of the Vineland Adaptive Behavior Scales for communication, daily living skills, socialization and motor skills, and the Vineland composite standard score.
Statistical Considerations (sample size and analysis plan):	The sample size (number of enrolled subjects) will be large enough to detect trends and differences. The primary analysis for Syner-G therapy will use the intention-to-treat (ITT) population and evaluate overall survival based on chronological patient age. Median survival will be compared to previously reported natural history studies of infantile and juvenile gangliosidoses. For rate of change in neurocognitive functioning over the duration of follow-up, using general estimating equations (GEE) and an exchangeable working correlation structure, variance estimation for confidence intervals and p-values will take into account the possible correlated nature of multiple measurements on the same individual. Supportive analyses will include evaluation using the per-protocol (PP) population. Subgroup analyses: analyses will be repeated separately among the infantile and juvenile forms of both GM1 and GM2 gangliosidosis.
Sponsors (federal, state, foundation and industry support):	National Institutes of Health (NIH)

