12.0 Study Objectives

12.1 Primary objective. The primary analysis for Syner-G treatment regimen will use the intention-to-treat (ITT) population and evaluate overall survival. This will be evaluated based on chronological age at time of death or conclusion of study (whichever occurs first), and compared to available natural history data. Median survival will be compared to previously reported natural history studies of infantile⁹ and juvenile¹¹ forms. Median survival of patients with infantile GM2 gangliosidosis was estimated at 47 months based on data from the National Tay-Sachs and Allied Diseases database for patients born after 2000.⁹ Median survival for the juvenile form was estimated at 14.5 years.¹¹

12.2 Secondary objective. Evaluate the effect of Syner-G therapy in patients with infant and juvenile gangliosidoses on changes in neurodevelopmental status, as assessed using age-equivalent scores of the Bayley Scales of Infant and Toddler Development for expressive communication, receptive communication, fine motor skills and gross motor skills; and using the Vineland Adaptive Behavior Scales.

A secondary endpoint will be the rate of change (i.e., slope) in neurocognitive functioning over the duration of follow-up, compared to available natural history data. This analysis will be conducted separately for each of the two sub-types: infantile and juvenile. The primary neurocognitive functioning endpoint for both pediatric groups is age-equivalent scores of the Bayley Scales of Infant and Toddler Development for expressive communication, receptive communication, fine motor skills and gross motor skills. Another primary neurocognitive functioning endpoint for both pediatric groups is age-equivalent scores of the Vineland Adaptive Behavior Scales. Using general estimating equations (GEE) and an exchangeable working correlation structure, variance estimation for confidence intervals and P-values will take into

account the possible correlated nature of multiple measurements on the same individual. Supportive analyses will include evaluation using the per-protocol (PP) population.

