13.2 Study population. Study population will be any patient with an infantile or late-infantile/juvenile gangliosidosis disease.

13.3 Sample size. A total of 30 infants or children:

- 5 patients with infantile Tay-Sachs disease
- 5 patients with juvenile Tay-Sachs disease
- 5 patients with infantile Sandhoff disease
- 5 patients with juvenile Sandhoff disease
- 5 patients with infantile GM1 gangliosidosis
- 5 patients with juvenile GM1 gangliosidosis

13.4 Subject recruitment. Subjects will be recruited from the investigators' clinical practice and through the Lysosomal Disease Network. This clinical trial will be posted on ClinicalTrials.gov and this may serve to recruit patients to the study.

13.5 Subject screening. Eligibility will be assessed during a baseline evaluation and will include confirmation of gangliosidosis disease via mutation analysis and tissue (e.g. leukocyte) ascertainment of level of hexosaminidase or β -galactosidase enzyme activity.

13.6 Prior and concomitant therapy. Subjects may have had previous therapies for gangliosidosis. If subjects are taking miglustat and/or pyrimethamine, and/or are on a ketogenic diet at the time of screening, they will be allowed to continue these therapies and will be allowed to participate in the Syner-G study.

13.7 Inclusion criteria. Subjects will be eligible to participate in the study if all of the following criteria are met: 1) confirmed diagnosis of infantile or juvenile GM1 or GM2 gangliosidosis via mutation analysis and tissue enzyme activity analysis (e.g. leukocyte activity of β -hexosaminidase A, including percent activity contributed from both α -subunit and β -subunits) or tissue β -galactosidase enzyme activity; 2) subjects must be age 0 - 17 years at time of enrollment; and 3) subjects and their caregivers must work closely with their University of Minnesota ketogenic diet team, and with their local ketogenic diet team, which must include a ketogenic dietician and a neurologist trained in the ketogenic diet.

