18.0 Data Analysis

18.1 Subject populations for analysis:

- Intention-to-treat Population (ITT): All subjects who initiate any portion of the treatment regimen in association with this study
- Per-protocol Population (PP): Includes all subjects who initiate treatment and are compliant with at least 75% of prescribed drug doses of miglustat, and at least 3:1 ketogenic diet.
- Safety population: All subjects who receive any amount of the combination treatment regimen. Due to the nature of a combination treatment, multiple groups may be identified, should partial adherence be observed.

18.2 Sample size determination. The sample size for the study was determined primarily by feasibility due to the extremely rare nature of the disease. There are two distinct sub-types to be evaluated: infantile and juvenile. Analysis will be based on variability estimates from published natural history studies^{8,11,19} of the infantile form and juvenile form, and correlation between baseline and annual follow-up for up to 4 years.

18.3 Statistical analysis. Descriptive analyses of baseline characteristics and outcomes will include means, standard deviations, medians, and ranges for continuous variables and frequencies for categorical variables. Treatment compliance for each group will also be evaluated. All analyses will be conducted separately for the two disease sub-types – infantile and juvenile – due to the highly heterogeneous patient groups.

The primary analysis for Syner-G treatment regimen will use the intention-to-treat (ITT) population and evaluate overall survival. This will be evaluated based on chronological age at time of death or conclusion of study (whichever occurs first), and compared to available natural history data. Median survival will be compared to previously reported natural history studies of infantile⁹ and juvenile¹¹ forms. Infantile median survival was estimated at 47 months based on data from the National Tay-Sachs and Allied Diseases database for patients born after 2000.⁹ Median survival for the juvenile form was estimated at 14.5 years.¹¹

A secondary endpoint will be the rate of change (i.e., slope) in neurocognitive functioning over the duration of follow-up, compared to available natural history data. This analysis will be conducted separately for each of the two sub-types: infantile and juvenile. The primary

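### The Synopsis says the sample is large enough to detect differences, but no calculation supports this; juvenile survival cannot meet it for a halved hazard, and moderate infantile effects are unsupported

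*Combined protocol and SAP*

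**What the plan says.** The Synopsis, under Statistical Considerations, asserts: "The sample size (number of enrolled subjects) will be large enough to detect trends and differences". It attaches no effect size, significance level or power.

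Section 18.2 gives a different basis: "The sample size for the study was determined primarily by feasibility due to the extremely rare nature of the disease". It goes on to mention variability estimates and "correlation between baseline and annual follow-up for up to 4 years", but gives no value for either.

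Section 13.3 sets the size: "A total of 30 infants or children", in six diagnostic groups of five, which makes 15 infantile and 15 juvenile. Section 18.3 adds: "All analyses will be conducted separately for the two disease sub-types". Overall survival is the primary analysis, and median survival is compared with published figures. Section 12.1 supplies them: "Median survival of patients with infantile GM2 gangliosidosis was estimated at 47 months" and "Median survival for the juvenile form was estimated at 14.5 years". No test is named.

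On timing, the Synopsis gives "Rolling enrollment of patients with infantile or juvenile gangliosidosis over the next five years" and a study duration of five years. The schedule in section 17.0 has visits through Years 2–5.

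**The concern.** The Synopsis and section 18.2 describe the same 30 children in ways that do not agree: one promises an ability to detect differences, the other says the number was what could be recruited. A feasibility-based size is legitimate in a disease this rare. A promise of sensitivity with nothing behind it is a different matter.

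The primary endpoint counts deaths, and information on survival comes from deaths rather than from enrolled children. With 15 children per sub-type, a median of 14.5 years in one of them and at most about five years of observation, deaths will be few. If the Synopsis claim stands, a juvenile comparison that finds nothing could be taken to mean that the regimen does not prolong survival, when the design had little chance of showing that it did.

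**Working it through.** **Plan's own figure.** There is nothing to reproduce. Thirty is 6 × 5; no alpha, power, effect or event target is stated.

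**Inputs from the documents.** n = 15 per sub-type (13.3, 18.3); medians 47 months and 14.5 × 12 = 174 months (12.1); five-year enrolment and five-year duration (Synopsis).

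**Assumptions, none of them in the documents.** Entry age uniform on 6–24 or 12–36 months (infantile) and on 3–12 or 5–14 years (juvenile). Weibull survival in age with shape 1 to 3, fixed to the stated median and conditional on being alive at entry. No dropout. Follow-up either uniform on 0–60 months (even entry, calendar stop at five years) or 60 months for every child.

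**Expected deaths, simplest case (shape 1).** Let x = ln 2 × 60 / median.
- Infantile: x = 0.885. Uniform entry: 15 × [1 − (1 − e^−x)/x] = 15 × 0.336 = 5.0. Five years each: 15 × (1 − e^−x) = 8.8.
- Juvenile: x = 0.239. Uniform entry: 15 × 0.111 = 1.7. Five years each: 3.2.

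A hazard that rises with age (shape above 1) increases these counts.

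**Power.** One-sample log-rank test, z = (O − E)/√E, significant if z < −1.96. Figures are simulated (20,000 or more trials per scenario) and good to about one percentage point; ranges run over shape and entry age.

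| Follow-up | Sub-type | Expected deaths, natural history | Power, hazard ratio 0.5 |
|---|---|---|---|
| Uniform five-year entry | Infantile | about 5–8 | about 15–39% |
| Uniform five-year entry | Juvenile | about 1.7–3 | 0–3% |
| Five years each | Infantile | about 9–15 | about 34–70% |
| Five years each | Juvenile | about 3–6 | 0–19% |

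For a hazard ratio of 0.33, infantile power is 69–97% with five full years each, and about 33–73% with uniform entry.

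**Cross-check without simulation.** Events needed for 80% power at two-sided 5%, by the normal approximation, are (1.96 + 0.842)² / (ln HR)². For HR 0.5 this is 7.85 / 0.480 = 16.3, so 17, more than the 15 children in either sub-type.

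**Juvenile floor.** Treat the death count as Poisson. With 2 expected deaths, P(0) = e^−2 = 0.135; with 3, e^−3 = 0.050. Both exceed 0.025, so even no deaths at all would not be significant. Zero deaths becomes significant only when the expected number passes ln 40 = 3.7.

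**Precision.** Exact Poisson 95% limits for observed/expected deaths when the two are equal: 2 deaths, 0.12 to 3.61; 7 deaths, 0.40 to 2.06; 12 deaths, 0.52 to 1.75.

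**Sensitivity to the juvenile benchmark.** With a 10-year median, shapes 1.5–3 and uniform entry, expected juvenile deaths rise to 3.1–6.4, and power for HR 0.5 to about 5–24%.

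**The case against.** **A reader might infer that the claimed property is disproved.** The documents do not support that. The Synopsis names no target difference, so the sentence is unsupported rather than shown false in general, and a very large infantile effect could be detected with full follow-up. The sentence also covers the neurocognitive slopes, which death counts do not address. No variability or correlation value is given from which to check them.

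**A reader might take the death counts as properties of the plan.** They are not. Accrual pattern, entry age, hazard shape and dropout are all unstated, and the eligible age range is only 0–17 years.

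**A reader might conclude that mean follow-up must be about two years.** That holds only if five years is a calendar limit and entry is even. The visit schedule and the reference to up to four years of annual follow-up allow longer observation per child. Sections 13.6 and 17.0 also expect some children to be on treatment already, which could mean early entry. Hence both scenarios are shown.

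**A reader might assume five children in every subgroup.** The recruitment groups are of five, but the planned subgroups within a sub-type are GM2 with 10 and GM1 with 5.

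**The test is an assumption and is conservative.** With uniform entry its actual one-sided size is about 1.0–1.3% (infantile) and 0–0.4% (juvenile), against a nominal 2.5%. A less strict normal approximation, with power Φ(√d × |ln HR| − 1.96) for d deaths, gives 40–50% at HR 0.5 for 6–8 infantile deaths and 16–22% for 2–3 juvenile deaths. That is better, but still low.

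**The benchmarks are imperfect.** Both medians come from GM2 sources, while 5 of the 15 children per sub-type have GM1. Section 1.1.4 also says that nearly half of the juvenile patients died in the first decade, which sits awkwardly with a 14.5-year median. A shorter median raises the juvenile figures, as shown, without bringing them near 80% for HR 0.5.

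Finally, section 18.2 already discloses feasibility, and its wording leaves room for other considerations. No passage says how a null juvenile result would be read. These points stand and limit the conclusion to the Synopsis claim itself. They do not supply the missing calculation.

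**Conclusion.** The Synopsis claim has no calculation behind it and does not agree with section 18.2. For juvenile survival it is not met: at the stated median, power to detect a halved hazard is at most about 19% even with five years of follow-up for every child, and close to zero with even five-year entry. For infantile survival it is unsupported for moderate effects: power for a halved hazard is about 15–39% or 34–70%, depending on follow-up. Only an effect near a hazard ratio of 0.33 is within reach, chiefly if every child has five years.

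These sizes rest on assumed entry ages, Weibull shapes 1–3, no dropout, the two GM2-based medians and a conservative one-sample log-rank test. The direction holds in every scenario run; the exact figures do not transfer to other assumptions. Nothing here judges the neurocognitive slopes.

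**What to change.** 1. Replace the Synopsis sentence with the feasibility statement of section 18.2.
2. In 18.2, name the assumptions on accrual, entry age, hazard shape and dropout, and say whether five years is calendar time or follow-up per child. Under those assumptions give, as ranges for each sub-type, the expected deaths and the expected confidence interval for observed/expected deaths.
3. State that juvenile survival is descriptive and that a non-significant juvenile result is not evidence of no effect.

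The cost is wording in the Synopsis and analysis section plus a short calculation. Enrolment, treatment and data collection do not change. The downside is that the stated claim becomes less favourable.

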1.0 Disease Overview

The gangliosidoses are fatal genetic conditions inherited in an autosomal recessive pattern. The GM2 gangliosidoses are caused by mutations to the genes that encode production of the lysosomal enzymes hexosaminidase A and hexosaminidase B, causing Tay-Sachs disease and Sandhoff disease, respectively. Without these enzymes individuals cannot catalyze the biodegradation of GM2 ganglioside.

The GM2 gangliosidoses disease have an estimated overall occurrence rate of 1:200,000 live births for Tay-Sachs disease, and 1:400,000 live births for Sandhoff disease.¹ The carrier rate for GM2 gangliosidosis diseases in the general population is estimated to be 1:250.^{1,2} Among Ashkenazi Jews, French Canadians, and Louisiana Cajuns the incidence rate is much higher, with overall elevated incidence rates of 1 in 27 persons thought to be a genetic carrier for a GM2 gangliosidosis disease (Tay-Sachs disease and Sandhoff disease).²

Before the advent of population-based carrier screening, education, and counseling programs for the prevention of Tay-Sachs disease in Jewish communities, the incidence of Tay-Sachs disease was about one in 3,600 Ashkenazi Jewish births. Currently, due to increased screening and awareness, the incidence of Tay-Sachs in Ashkenazi Jews of North America has been reduced by greater than 90%.^{1,3} Although the incidence of Tay-Sachs disease has significantly declined in the Jewish community, the disease has been reported in children of virtually all ethnic, racial and religious groups. Irish Americans have a 1 in 50 chance of a person being a carrier. Sandhoff disease, unlike Tay-Sachs, occurs more commonly in non-Jewish populations.^{1,4}

GM1 gangliosidosis is caused by mutations to the gene that encodes β -galactosidase, leading to deficiency of β -galactosidase. Without the β -galactosidase enzyme to break it down, ganglioside accumulates in neuronal cells and other tissues, leading to mental and physical deterioration. The worldwide prevalence of GM1 gangliosidosis is estimated to be 1:100,000 to 200,000 live births.¹ In Malta and Brazil, and in the Roma and Cypriot populations, a high prevalence of GM1 gangliosidosis has been found.⁵

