A survey based study of 316 patients with infantile GM2 gangliosidosis (survey-based data from 92 patients, data from 103 patients in the National Tay-Sachs and Allied Diseases patient advocacy group's database, and 121 patients reported in the literature), it was noted that in infantile GM2 gangliosidosis, the most common onset symptoms were developmental delay, startle-response and hypotonia.⁹ Among the 92 patients surveyed, there were few differences noted in phenotype between infantile Tay-Sachs disease and infantile Sandhoff disease, although a tendency was observed for visual problems, seizures and movement abnormalities to occur earlier in the patients with Tay-Sachs disease.⁹ As the disease advanced, seizure management often became the primary focus of clinical care.⁹

In the study by Maegawa et al. the mean onset of symptoms in juvenile GM2 gangliosidosis was reported as 5.3 ± 4.1 years, with gait disturbances, incoordination, speech difficulties and developmental delay being the most common symptoms noted at onset.¹¹ Neuropathy and psychiatric disturbances were found to be more common in patients with juvenile Sandhoff disease compared to juvenile Tay-Sachs disease.¹¹ In patients with juvenile Sandhoff disease, sleep problems, diarrhea and constipation were observed to be more common than in the patients with juvenile Tay-Sachs disease.¹¹ Dysphagia, sphincter incontinence and sleep problems were more common at the time of symptom onset in Tay-Sachs disease.¹¹ But this study found no other statistically significant differences between the patients with juvenile Tay-Sachs disease compared to patients with juvenile Sandhoff disease.¹¹

1.1.4 Natural history survival data in infantile and juvenile gangliosidosis. The study by Bley et al. showed the median age of death in the infantile form was 47 months.⁹ The case histories of 155 patients with juvenile GM2 gangliosidosis that were reviewed by Maegawa et al. were found to have a median survival of 14.5 years.¹¹ Nearly half of the patients died within the first decade of life, and roughly 25% of the patients lived into their late teens.¹¹ No statistically significant differences were found between the patients with Tay-Sachs disease and those with Sandhoff disease.¹¹

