neurocognitive functioning endpoint for both pediatric groups is age-equivalent scores of the Bayley Scales of Infant and Toddler Development for expressive communication, receptive communication, fine motor skills and gross motor skills. Another primary neurocognitive functioning endpoint for both pediatric groups is age-equivalent scores of the Vineland Adaptive Behavior Scales. Using general estimating equations (GEE) and an exchangeable working correlation structure, variance estimation for confidence intervals and P-values will take into account the possible correlated nature of multiple measurements on the same individual. Supportive analyses will include evaluation using the per-protocol (PP) population.

Safety analyses will be primarily descriptive, reporting the number and percentage of AEs and descriptive summaries. These analyses will use multiple safety populations according to which components of the combination therapy subjects were exposed to. Due to the longitudinal nature of the study and potential for later-emerging effects, the safety profile will be characterized for each sub-type over time. Supportive analyses will include evaluation using the PP population.

Subgroup analyses: analyses will be repeated among GM1 gangliosidosis patients and among GM2 gangliosidosis patients, and among the infantile and juvenile forms of both GM1 and GM2 gangliosidosis.

18.4 Missing data. Despite best efforts to avoid missing data, it is possible that some will occur and will be a potential limitation to the interpretation and generalizability of results. In particular, missing data may arise for non-survival outcomes (e.g. neurocognitive function data) in the event of death. For these instances, it is unclear whether a complete-case analysis (i.e. excluding patients who die) would be unbiased, and therefore would be unsatisfactory. It is also unclear what would be an appropriate magnitude of discount to satisfactorily represent the negative outcome of death. By conducting both the complete-case analysis (unbiased if death is independent of the non-survival outcome) and an analysis with an imputed value for instances of death (intention-to-treat type of analysis), the potential magnitude of treatment effect will be better characterized.

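### The slope variance allows for correlation within a child only, so intervals would be too narrow if affected siblings enrol in the same stratum with positively correlated slopes

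*Combined protocol and SAP*

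**What the plan says.** The slope of neurocognitive function is analysed "using general estimating equations (GEE) and an exchangeable working correlation structure" (Synopsis, Statistical Considerations). The variance rule given there is that "variance estimation for confidence intervals and p-values will take into account the possible correlated nature of multiple measurements on the same individual". Sections 12.2, 13.1 and 18.3 say the same. No family level appears in section 18, and the Schedule of Events (section 17) lists demographic data at baseline without mentioning a family identifier.

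On who may enter, 13.2 states: "Study population will be any patient with an infantile or late-infantile/juvenile gangliosidosis disease". Section 13.4 adds: "Subjects will be recruited from the investigators' clinical practice and through the Lysosomal Disease Network". The three inclusion criteria (13.7) and five exclusion criteria (13.8) do not mention relatedness, and 24.4 says that everyone with these disorders will be considered.

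On inheritance, section 1.0 states: "The gangliosidoses are fatal genetic conditions inherited in an autosomal recessive pattern".

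The slope analysis is run separately for infantile and juvenile disease. If the targets in 13.3 are met, each stratum holds 3 × 5 = 15 children. The planned infantile GM2 and juvenile GM2 subgroups hold 2 × 5 = 10 each, and the infantile GM1 and juvenile GM1 subgroups hold 5 each.

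**The concern.** A robust GEE variance is valid when the clusters are independent. The plan makes the child the cluster, so two affected siblings count as two independent pieces of information. In a recessive disease, full siblings who are both affected carry the same disease genotype, and they would normally share a home and a local diet team. Similar rates of decline are therefore plausible, and the second sibling then adds less information than the variance assumes.

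Enrolment of siblings is also plausible. Recruitment runs over five years from a specialist practice and a disease network, ages 0 to 17 are accepted, and section 17 stresses collecting as much data as possible because the disease is rare. For juvenile GM2 disease, section 1.1.3 says that "the mean onset of symptoms in juvenile GM2 gangliosidosis was reported as 5.3 ± 4.1 years", which leaves time for a second affected birth before the first child is diagnosed.

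At stake are the confidence intervals and P-values for the slope. With about 15 children per stratum, a few sibling pairs make up a sizeable share of the data. The point estimate is not the issue.

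**Working it through.** **The plan's own figure.** There is no power, alpha, effect size or standard deviation for the slope to reproduce. The only design figure is N = 6 × 5 = 30 (13.3), set by feasibility (18.2).

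**Inputs from the documents.** n = 15 per stratum, 10 per infantile or juvenile GM2 subgroup, 5 per disease-by-form group (13.3); up to 1 + 4 = 5 annual measurements per child (18.2).

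**Inputs assumed.** Number of sibling pairs p in the same stratum; correlation rho between siblings' estimated slopes. Both are varied below.

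**Step 1: formula.** With p pairs among n children, the variance of the mean slope is multiplied by

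DEFF = 1 + (2p/n) × rho.

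The true standard error is √DEFF times the one reported under child-level clustering. The actual coverage of a nominal 95% interval is 2Φ(1.96/√DEFF) − 1.

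**Step 2: one case in full.** n = 15, p = 3, rho = 0.5: DEFF = 1 + (6/15) × 0.5 = 1.20; √1.20 = 1.095; 1.96/1.095 = 1.79; coverage 92.6%.

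**Step 3: the range.**

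| n | pairs | rho | DEFF | true SE above reported | coverage |
|---|---|---|---|---|---|
| 15 | 0 | any | 1.000 | 0% | 95.0% |
| 15 | any | 0 | 1.000 | 0% | 95.0% |
| 15 | 1 | −0.2 | 0.973 | −1.3% | 95.3% |
| 15 | 1 | 0.25 | 1.033 | 1.7% | 94.6% |
| 15 | 1 | 0.5 | 1.067 | 3.3% | 94.2% |
| 15 | 1 | 1 | 1.133 | 6.5% | 93.4% |
| 15 | 2 | 0.5 | 1.133 | 6.5% | 93.4% |
| 15 | 3 | 0.5 | 1.200 | 9.5% | 92.6% |
| 15 | 7 (maximum) | 0.5 | 1.467 | 21% | 89.4% |
| 10 | 1 | 0.5 | 1.100 | 4.9% | 93.8% |
| 10 | 3 | 0.5 | 1.300 | 14% | 91.4% |
| 5 | 1 | 0.5 | 1.200 | 9.5% | 92.6% |
| 5 | 2 | 0.5 | 1.400 | 18% | 90.2% |

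**Step 4: does clustering on family repair it?** Simulation with 20,000 runs, 5 annual visits, an assumed slope SD of 1 and residual SD of 1, and balanced data, so that the GEE slope is the mean of the child slopes. Pairs have slope correlation 0.5. The corrected version multiplies the variance by G/(G − 1) and uses a t quantile on G − 1 degrees of freedom, where G is the number of clusters. Read the results to about half a percentage point.

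| n | pairs | uncorrected: child → family | corrected: child → family |
|---|---|---|---|
| 15 | 0 | 91.9% (same) | 94.9% (same) |
| 15 | 1 | 91.2% → 91.5% | 94.5% → 94.8% |
| 15 | 3 | 89.2% → 90.4% | 92.6% → 94.1% |
| 15 | 7 | 85.6% → 88.6% | 89.8% → 94.9% |
| 5 | 0 | 84.4% (same) | 95.1% (same) |
| 5 | 2 | 77.3% → 73.4% | 91.3% → 94.5% |

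Family clustering without the correction gains little, and at n = 5 with two pairs it makes coverage worse. The correction without family clustering leaves 92.6% and 89.8% at n = 15 with three and seven pairs. Both parts are needed.

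**The case against.** The strongest reply is that the defect depends on events the documents do not predict. Nothing says that siblings will enrol or how many. Section 1.0 gives birth rates of 1:200,000 for Tay-Sachs disease and 1:400,000 for Sandhoff disease. Section 1.1 says that death in the infantile form often comes by three to four years, so two affected infants would have to be alive and enrolled together. The onset figure in 1.1.3 concerns juvenile GM2 only and lends no support to infantile pairs. All of this stands, and zero pairs is a realistic outcome.

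A second reply is that having few clusters matters more. An uncorrected robust variance covers only about 92% at n = 15 and 84% at n = 5 with no siblings at all, and the plan names no small-sample correction. This also stands. It is a reason to make both changes together, since the correction alone does not deal with several correlated pairs.

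A third reply is that the factors making siblings alike are partly weak. The University of Minnesota diet team serves every subject, so it does not distinguish families. A reader might also infer a shared caregiver rater, but the documents do not describe one, and Appendix 2 assigns testing to neuropsychologists. Measurement noise over a few annual visits also dilutes the correlation between estimated slopes. What remains is mainly shared genotype, which makes a positive correlation plausible without fixing its size.

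**Conclusion.** The point holds as a conditional, minor one. The stated rule ignores dependence between siblings, and nothing in the eligibility criteria rules that dependence out. The intervals are too narrow if three things hold together: siblings enrol, they fall in the same analysis stratum, and their slopes are positively correlated. Under an assumed correlation of 0.5 at n = 15, the standard error is understated slightly with one pair and materially with three or more. The subgroups of 10 and 5 are more sensitive.

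A reader might infer that the intervals are too narrow whenever siblings take part, or that the trial's P-values are already known to be too optimistic. The documents support neither: they give no count of pairs and no correlation, and a correlation of zero or below removes or reverses the effect. Nor should the less favourable rows of the table be read as the error rates of this plan. They start from a test that is exact without siblings, and the plan states no alpha and no small-sample method.

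The endpoint is secondary, and the primary survival comparison is not affected by this wording.

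**What to change.** - Add a family identifier to the demographic data collected at baseline. It is easiest to capture at enrolment.
- In the Synopsis, 12.2, 13.1 and 18.3, state that the variance allows for correlation among repeated measurements on a child and among children of the same family. Keep the exchangeable working correlation within child. Extending it to the whole family would set the correlation between siblings equal to that within a child.
- Compute the robust variance with family as the cluster, and in the same sentence specify a small-sample correction with degrees of freedom based on the number of families. The two should not be separated.
- Optionally, add a sensitivity analysis with one child per family, chosen by a rule fixed in advance.

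**Cost.** One baseline field and one sentence in four places, with no extra children or visits. Intervals become wider. Part of this comes from the small-sample correction even if no siblings enrol: compared with an uncorrected normal interval at n = 15, the factor under the correction used above is 2.145 × √(15/14) / 1.96 = 1.13, that is, 13% wider. With no siblings, the point estimate and the uncorrected robust variance are the same as under the present rule.
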